7.1.2.5. Statistical Analyses/Methods

Hgb Efficacy Co-Primary Statistical Analyses
Endpoint(s)

 • Mean change in Hgb between baseline and EP
Model Specification

 • Hgb during the EP will be defined as the mean of all available post-randomization Hgb values (on and off-treatment) during the EP (Week 28-52). • The ANCOVA model used to quantify the difference in mean Hgb change will adjust for the following baseline values: 
 ○ Treatment ○ Baseline Hgb (see Section 10.5.2) ○ Current ESA use (as randomized, see Section 10.10.2) ○ Region (as randomized, see Section 10.9 & Section 10.10.2)
Multiple Imputation Analysis

 • Multiple imputation analysis will be performed using all available Hgb values (on and off-treatment) and conducted under a set of assumptions about missing Hgb values (see Section 10.6.3). 
 ○ Intermittent missing post-baseline scheduled Hgb data in both arms through Week 52 will be imputed using PROC MI procedure with NIMPUTE = 200 and MCMC IMPUTE = monotone to generate 200 datasets with only monotone missing patterns. Burn in iterations (NBITER) and maximum iteration (MAXITER) will both be set to 500. The seed for reproducibility is set to 200808. The imputations will be done by randomized treatment, current ESA use at randomization, and region. ○ For each of the monotone missing dataset (out of the 200 imputed as indicated above), the missing scheduled Hgb values through Week 52 will be imputed based on the MAR assumption and will be performed using PROC MI by treatment, current ESA use at randomization, and region. The monotone regression will have baseline Hgb, prior scheduled (possibly imputed) Hgb values, and may include current ESA use at randomization and region as covariates (see Model Checking & Diagnostics, below).

Hgb Efficacy Co-Primary Statistical Analyses

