
 Subgroup analysis will be performed using all available observed and imputed Hgb values (on and off-treatment), Rubin’s rules [Rubin, 1987] will be used to combine results of the imputed datasets using SAS PROC MIANALYZE procedure. Subgroup analysis will also be performed separately using evaluable Hgb values only (see Section 10.6.3). Subgroup analysis details are discussed in Section 10.10.1.

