10.6.3. Efficacy

10.6.3.1. Hemoglobin Endpoints

Hemoglobin Values
Central Laboratory and HemoCue Hgb Values

 ● When source of Hgb measurement is not specified: 
 ○ For reporting purposes, central laboratory Hgb values will be used, unless otherwise specified. However, if a central laboratory Hgb value is missing, a corresponding non-missing HemoCue Hgb value will be used. This approach will

Hemoglobin Values

be used for the co-primary Hgb analysis.
 
 Some displays may be created for either central laboratory Hgb values only or HemoCue Hgb values only. The central laboratory summary will be considered the primary summary in this case.
Evaluable Hemoglobin Values

 Evaluable Hgb values are on-treatment Hgb values (see Section 10.4.1) that are not taken within the 8 weeks following a red blood cell transfusion, a whole blood transfusion, or a non-randomized ESA treatment which occurs on or after the randomization date. Red blood cell transfusions, whole blood transfusions and non-randomized ESA treatments occurring on or after the randomization date are identified by comparing the start and stop date of the respective transfusion or ESA concomitant medication record to the randomization date.
Imputed Hemoglobin Values

 For each missing value between baseline to Week 52 (inclusive), 200 imputed values will be generated using the multiple imputation method (see Section 7.1.2). The average of these 200 imputed values will be used as the value for this missing value in the summary tables and figures. For co-primary efficacy Hgb analysis and the corresponding subgroup analyses using all available observed and imputed Hgb values (on and off-treatment), Rubin's rules [Rubin, 1987] will be used to combine results of the imputed datasets using SAS PROC MIANALYZE procedure.
EP Hemoglobin Value for Co-primary Hgb Analysis

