10.10. Appendix 10: Examination of Covariates, Subgroups & Other Strata

10.10.1. Handling of Covariates, Subgroups & Other Strata

- The following is a non-exhaustive list of covariates that may be used in summaries of demographics, descriptive summaries and statistical analyses.
- Additional covariates of clinical interest may also be considered.
- If the percentage of subjects is small within a particular subgroup, then the subgroup categories may be refined prior to unblinding the trial.
- If the category cannot be refined further, then descriptive rather than statistical comparisons may be performed for the particular subgroup. If there are less than 25 subjects in one of the subgroup categories, any subgroup statistical comparison should be interpreted with caution.
- A pre-specified strategy for prioritizing subgroups/covariates is defined below (as recommended in the 2015 draft Committee for Medicinal Products for Human Use (CHMP) guidance on the investigation of subgroups in confirmatory clinical trials)
- The co-primary and principal secondary endpoints will be evaluated for the subgroups below. Although subgroup analyses are aimed to assess for consistency with the overall results, they may have low power, especially if the subgroup is small or has a low number of events. Statistical models (Cox Proportional Hazards or ANCOVA) will be adjusted for the covariates used in the original analysis, subgroup, treatment and treatment by subgroup interaction. For the prognostic randomization stratification factors (region and current ESA use), the actual status of the factor derived from the eCRF will be used (see Section 10.10.2). For the subgroup Regions combined (USA vs. non-USA), the randomization stratification factor Region (with 5 levels, Regions 1- 5) will not be included in the statistical model. For the subgroup analyses by baseline Hgb group (categorical), the baseline Hgb (continuous) will not be included in the statistical model.

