- Please note that if any of the models still fail to converge after Step 3, model-adjusted analyses will not be performed. The associated descriptive statistics will be displayed. If the original model fails to converge, but it converges after one of the three steps, the output will display the changes made to the original model in a footnote. When a subgroup category assesses the same or a similar parameter (e.g., country is similar to region) as one of the prognostic stratification variables, the randomization stratification variable will be removed from the model.
- Point estimates and two-sided 95% CIs will be estimated within subgroups, the subgroup by treatment interaction two-sided p-value will be calculated and subgroup results will be graphically presented (e.g. Forest Plots). Directional consistency in subgroup treatment effects and a non-significant interaction p-value (two-sided 10% level) would support that the overall treatment effect is broadly applicable to the full study population. Subgroup analyses will not be adjusted for multiplicity.

Category	Covariates and / or Subgroups	Summary of Demographics & Baseline Characteristics Note: Include 'Missing' categories, if applicable.	Subgroup Analysis for Co-primary MACE & Principal Secondary Safety Endpoints Note: Do not include 'Missing' categories.	Subgroup Analysis for Co-primary Hgb Endpoints Note: Do not include 'Missing' categories.
Key Covariates/Subgroups of Regulatory/Clinical Interest or Potential Biological Plausibility for Different Subgroup Effects				
Age (years)	Summary statistics of continuous values	Yes	No	No
Age at randomization (Grouping 1)	< 65 years, 65-<75 years, ≥75 years	Yes	Yes	Yes
Age at randomization (Grouping 2)	≤18 years, 19 - 64 years, ≥65 years	Yes	No	No
Age at randomization (Grouping 3)	18-64 years, 65 - 84 years, ≥ 85 years	No (included in stand-alone age ranges table)	No	No
Gender	Female, Male	Yes	Yes	Yes
Ethnicity	Hispanic or Latino, Not Hispanic or Latino	Yes	Yes	Yes
High level race	American Indian or Alaskan Native Asian Black or African American Native Hawaiian or Other Pacific Islander White Mixed Race	Yes	Yes	Yes
Race detail	American Indian or Alaskan Native Asian – Central/South Asian Heritage Asian – East Asian Heritage Asian – Japanese Heritage Asian – South East Asian Heritage	Yes	No	No

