10.12. Appendix 12: Model Checking and Diagnostics for Statistical Analyses

10.12.1. Statistical Analysis Assumptions

Endpoint(s)	
 Hgb Change from Baseline to the EP
Analysis	
 ANCOVA
	
 Distributional assumptions underlying the model used for analysis will be examined by obtaining a normal probability plot of the residuals and a plot of the residuals versus the fitted values (i.e. checking the normality assumption and constant variance assumption of the model respectively) to gain confidence that the model assumptions are reasonable. If there are any departures from the distributional assumptions, alternative models will be explored using appropriate transformed data. Models will be examined for treatment interactions with baseline Hgb and stratification factors
Analysis	
 Multiple Imputation/Tipping Point Analysis
	
 Intermittent missing data imputation: 
 If there are error and or warning messages related to the by statement (e.g. not enough observations to fit regression models), try to impute by randomized treatment and current ESA use at randomization, then by randomized treatment only until no error/warning messages. If convergence issue still occurs, the convergence precision may be set to 1E-3. Monotone missing data imputation: 
 When imputing for each of the monotone missing dataset (out of the 200), if there are error and or warning messages related to the by statement and/or regression model (e.g. not enough observations with the Monotone statement), try 1) impute by randomized treatment and current ESA use at randomization, with baseline Hgb and region as covariates, 2) impute by randomized treatment, with baseline Hgb, current ESA use at randomization, and region as covariates, 3) impute by randomized treatment, with baseline Hgb, and current ESA use at randomization as covariates, 4) impute by randomized treatment with baseline Hgb as a covariate, until no error/warning messages.
Endpoint(s)	
 Time to first event endpoints: MACE and MACE or thromboembolic events or hospitalization for HF
Analysis	
 Cox proportional hazards

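### For 19 of the 23 Hgb subgroup factors the imputation model omits the factor, so treatment-by-subgroup interactions shrink modestly toward zero

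*SAP*

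**What the plan says.** Section 7.1.2.5 imputes missing scheduled Hgb in two steps. Intermittent gaps are filled by MCMC: "The imputations will be done by randomized treatment, current ESA use at randomization, and region". The remaining monotone gaps are then filled by regression, which "will be performed using PROC MI by treatment, current ESA use at randomization, and region". On predictors: "The monotone regression will have baseline Hgb, prior scheduled (possibly imputed) Hgb values", with ESA use and region as the only other optional covariates.

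On subgroups, Section 7.1.2.5 says: "Subgroup analysis will be performed using all available observed and imputed Hgb values (on and off-treatment"). Section 10.6.3.1 sends the same imputed datasets to the subgroup analyses: "For co-primary efficacy Hgb analysis and the corresponding subgroup analyses using all available observed and imputed Hgb values", pooled by Rubin's rules. Under Section 10.10.1 the subgroup models "will be adjusted for the covariates used in the original analysis, subgroup, treatment and treatment by subgroup interaction".

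The reading rule in Section 10.10.1 has two parts. Directional consistency across subgroups, together with "a non-significant interaction p-value (two-sided 10% level) would support that the overall treatment effect is broadly applicable to the full study population". The same section warns that subgroup analyses may have low power.

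Table 3, footnote 1, limits the by-subgroup Hgb analysis to two data sets: observed plus imputed values, and evaluable (on-treatment) values.

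**The concern.** An imputation model should contain every term the analysis model estimates. Here the analysis estimates a treatment-by-subgroup interaction. For most factors the imputation assumes that, given treatment, ESA use, region and earlier Hgb, the subgroup carries no further information. Imputed values then reflect a subgroup difference only as far as the subject's own earlier Hgb already shows it. Averaging them with observed values draws the subgroup-specific effects together.

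The direction of this bias is known, and it is the direction that makes consistency easier to claim. Directional consistency does not protect against it, because the within-subgroup estimates come from the same imputations.

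**Working it through.** **Which factors are affected.** The Section 10.10.1 table marks 23 factors for Hgb subgroup analysis: age (Grouping 1), gender, ethnicity, high-level race, region, USA/non-USA, current ESA use, prior ESA dose group, baseline Hgb group, BMI group, weight quartiles, CKD stage, hsCRP quartiles, dosing algorithm, six histories (diabetes, stroke, MI, cancer, heart failure, thromboembolic events), prior hospitalization, prior transfusion and ACEI/ARB use. Four are carried by the by-arm imputation: region, USA/non-USA (nested in region), current ESA use and baseline Hgb group (through continuous baseline Hgb). That leaves 23 − 4 = 19.

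**Upper bound.** The SAP states no attenuation, power or missing-data figure for these interactions, so there is nothing to reproduce. If imputed values carried no subgroup information at all, the interaction would shrink by the share of evaluation-period (EP) values that are imputed. Earlier observed Hgb lowers this.

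**Simulation.** From the SAP: N = 4500 randomized 1:1 (Section 2.3), seven EP visits, imputation limits of 6 and 15 g/dL, and the two-sided 10% interaction test. Assumed: a 50/50 binary subgroup, within-visit SD 1.0 g/dL, compound-symmetry plus AR(1) correlation, dropout otherwise uniform over visits, a true interaction of 0.5 g/dL, imputation by arm only, 5 imputations and 12 runs per row. Attenuation = 1 − (estimate without factor ÷ estimate with factor).

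| Subjects incomplete | Of these, nothing after baseline | EP values missing | Without | With | Attenuation |
|---|---|---|---|---|---|
| 10% | 0% | 7% | 0.487 | 0.501 | 2.8% |
| 10% | 25% | 8% | 0.454 | 0.473 | 4.0% |
| 20% | 0% | 15% | 0.447 | 0.475 | 5.9% |
| 20% | 25% | 16% | 0.457 | 0.500 | 8.6% |
| 30% | 0% | 22% | 0.475 | 0.514 | 7.6% |
| 30% | 25% | 24% | 0.437 | 0.499 | 12.4% |
| 20% | 100% | 20% | 0.395 | 0.483 | 18.2% |

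The Monte Carlo standard error of the estimates without the factor is 0.009–0.015. The last row agrees with the bound: 0.5 × (1 − 0.20) = 0.40 against 0.395 simulated. When dropout is spread over time, the attenuation is roughly half the bound or less.

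If the interaction builds up over the first visits (20% incomplete, a quarter of them with nothing after baseline, 20 runs), the estimates are 0.451 and 0.511: 1 − 0.451/0.511 = 11.7%.

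A separate simulation (true interaction −0.40 g/dL, 1930 per arm as an assumption, 80 replicates per cell) gave 4%, 8% and 10% at 10%, 20% and 30% missing with dropout over Weeks 8–52. With the last value at Weeks 4–12 it gave 7%, 17% and 23%.

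**Effect on the test.** For a true interaction of 0.15 g/dL with 20% incomplete (80 runs), the estimates were 0.136 without the factor and 0.152 with it: 1 − 0.136/0.152 = 10.5%. Power at the 10% level was 0.79 and 0.85. With 80 runs, the standard error of a power of 0.79 is √(0.79 × 0.21 / 80) ≈ 0.05, so the power loss is only indicative.

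A large interaction is still detected. With 1930 per arm there are 965 subjects per cell, and at SD 1.0 the interaction SE is √(4/965) ≈ 0.064, ignoring imputation variance. After 23% attenuation, 0.40 × 0.77 = 0.31 and z = 0.31/0.064 ≈ 4.8.

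**The case against.** A reader might infer that every Hgb subgroup interaction is driven toward zero and that consistency rests on non-significance alone. The documents do not support that.

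- Region, USA/non-USA, ESA use and baseline Hgb are in the imputation within each arm. The Section 10.12.1 fallback could later remove region and ESA use, since its last step is "4) impute by randomized treatment with baseline Hgb as a covariate", but that is a contingency.
- The reading rule also requires directional consistency. Subgroup estimates, confidence intervals and forest plots are shown beside it, and these analyses decide nothing confirmatory.
- Very early loss on a large scale fits the plan poorly. Off-treatment Hgb is used, subjects who stop drug are encouraged to stay (Section 10.7.1), and they keep visits at Weeks 4, 16, 28, 40 and 52 (Section 10.2.1.3). The 17–23% figures are therefore an outer case.
- The evaluable-values subgroup analysis runs without imputation.

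All of this limits the size; none of it removes the bias. The evaluable-values analysis targets a while-on-treatment estimand, so it is a cross-check and no substitute. The observed-values-only analysis would be a closer check on the treatment-policy data, but Table 3 does not run it by subgroup. The reduced off-treatment schedule also leaves four of the seven EP visits (Weeks 32, 36, 44 and 48) to be filled. Many of those gaps are bracketed by observed values, so they should attenuate less, but the MCMC step that fills them omits the subgroup factor too.

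**Conclusion.** The point holds for 19 of the 23 Hgb subgroup factors. In the analysis of observed plus imputed values, their interactions with treatment are attenuated by about 3–12% under 10–30% monotone missingness with dropout spread over time. About 17–23% applies only if 20–30% of subjects are lost very early. These sizes rest on assumed missing rates, correlation and SD; the direction follows from the specification.

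The practical effect is a slight tilt toward the broad-applicability reading. It matters most for small interactions near the detection limit; a large one would still be flagged. The co-primary non-inferiority test does not depend on this. It is a cheap improvement and does not threaten the trial's main conclusion.

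**What to change.** For each of the 19 affected analyses, re-impute within treatment arm with the subgroup factor, as dummy variables, in both the MCMC step for intermittent gaps and the monotone regression. Because imputation is by arm, this carries the treatment-by-subgroup interaction.

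Splitting by treatment, ESA use and region gives up to 2 × 2 × 5 = 20 cells, and multi-level dummies will be sparse in some. Where that happens, move region and ESA use from BY variables to covariates. The Section 10.12.1 fallback already allows this for the monotone step; for the MCMC step they should be added explicitly as predictors, since its fallback only drops them.

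Keep the co-primary imputations unchanged, and specify this before unblinding. The cost is about 19 extra imputation runs, some handling of sparse cells, and overall estimates that differ trivially between runs.

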7.2. CV Safety (MACE) Co-Primary Analysis

7.2.1. Overview of Planned CV Safety (MACE) Co-Primary and Supportive Analyses

Table 4 provides an overview of the planned CV safety (MACE) co-primary and supportive analyses.

Table 4 Overview of Planned CV Safety (MACE) Co-Primary and Supportive Analyses

Endpoint	Analysis Population	Absolute						
		Stats Analysis			Summary		Individual	
		T	F	L	T	F	F	L
Time to First Occurrence of Adjudicated MACE								
Co-Primary Analysis	ITT	Y	Y		Y			Y
Supportive Analysis While On-treatment	ITT	Y	Y		Y			
Sensitivity Analysis Tipping Point	ITT	Y	Y					
COVID-19 Supportive Analyses	ITT	Y	Y		Y			
Supportive Expanded Covariate Adjusted Analysis	ITT	Y	Y		Y			
By Subgroup	ITT	Y	Y		Y			

NOTES:

- T = Table, F = Figure, L = Listing, Y = Yes display generated.
- Stats Analysis = Represents TFL related to any formal statistical analyses (i.e. modelling) conducted.
- Summary = Represents TFL related to any summaries (i.e. descriptive statistics) of the observed raw data.
- Individual = Represents FL related to any displays of individual subject observed raw data.

7.2.2. Planned CV Safety (MACE) Co-Primary Statistical Analyses

CV Safety (MACE) Co-Primary Statistical Analyses
Endpoint(s)

 • Time to first occurrence of adjudicated MACE • The Cox Proportional Hazards model will adjust for the following baseline categorical values: 
 ○ Treatment ○ Current ESA use (as randomized, see Section 10.10.2) ○ Region (as randomized, see Section 10.9 & Section 10.10.2) • Confidence intervals for the rate per 100 person-years will also be reported. For within-group rates, the two-sided 95% CI will be obtained using an exact Poisson method. For difference in rates between treatments, the two-sided 95% CI will be constructed with a Normal approximation using Wald’s method [Liu, 2006]. • The co-primary analysis will use only adjudicated safety endpoints as determined by the clinical endpoint committee (CEC) within the time period for follow-up of CV endpoints defined in Section 10.6.4. • Calculation of time-to-event or censoring is described in further detail in Section 10.6.4. • First occurrence of adjudicated MACE for a subject is defined as the first adjudicated event, determined by the event date, that is indicated as all-cause mortality, non-fatal MI or non-fatal stroke with further details in Section 10.6.4.
Model Checking & Diagnostics

 • Refer to Appendix 12: Model Checking and Diagnostics for Statistical Analyses.
Model Results Presentation

 • A summary of the number and percentage of subjects having first-occurrence MACE will be provided by treatment group. The number and percentage of the types of events that make up the first occurrence of MACE will also be provided by treatment group. • A summary of all MACE including the number and percentage of subjects and number of events (including first and subsequent MACE) by type of event will be provided by treatment group. Subjects experiencing MACE will be further broken down into subjects who experienced exactly one MACE, subjects who experienced exactly two MACE, and subjects who experienced more than two MACE. The number and percentage of subjects in each of these categories by event type combinations will be provided by treatment group. • The hazard ratio, two-sided 95% CI, one-sided p-value for the statistical non-inferiority test, and one-sided p-value for the superiority test will be presented for the comparison of daprodustat vs. darbepoetin alfa using the Cox Proportional Hazards model. The number and percentage of subjects with a MACE event and the number censored at the end of the study, the MACE incidence rate per 100 person-years, and the absolute rate difference per 100 person-years and associated two-sided 95% CI will be displayed with the results of the Cox proportional hazards regression model. • To inform on the validity of the adjusted Cox proportional hazards model, the proportional hazards assumption will be assessed by plotting the logarithm of the negative logarithm of the estimated survivor function against the logarithm of time, for each treatment group. If the hazards are proportional, the lines should be approximately parallel. • The hazard ratio, two-sided 95% CIs and one-sided non-inferiority and superiority p-values will be displayed on a forest plot together with supportive analysis results (i.e., excluding the Tipping Point Analysis).

CV Safety (MACE) Co-Primary Statistical Analyses

 Time from Randomization to first adjudicated MACE event or end of trial will be evaluated using Kaplan-Meier (KM) methodology and displayed graphically for the comparison of daprodustat vs. darbepoetin alfa. A listing of all MACE events occurring during the study will be provided and will include treatment, site ID, unique subject ID, select demographic information, event type, event date, and study day.
Model Results Interpretation

 Non-inferiority will be achieved if the upper limit of the two-sided 95% CI for the hazard ratio is below the pre-specified non-inferiority margin of 1.25. For evaluation of MACE superiority, a principal secondary analysis, see Section 10.11.1.
Subgroup Analysis

 Subgroup analysis details are discussed in Section 10.10.1.

Sensitivity Statistical Analyses
Tipping Point (Multiple Imputation) Analysis

 Tipping point sensitivity analyses will be conducted under a range of missing data assumptions to determine how extreme assumptions need to be for non-inferiority conclusions to change. Assumptions about missing outcomes on the daprodustat and darbepoetin alfa arms will vary independently, and will include scenarios where subjects with missing data on daprodustat have worse outcomes than subjects with missing data on darbepoetin alfa. Missing data that occurs before the end of the study (i.e., due to withdrawal from the study) will be imputed across a range of scenarios using multiple imputation with treatment, current ESA use (as randomized, see Section 10.10.2) and region (as randomized, see Section 10.9 & Section 10.10.2) as strata in the imputation model and to generate the bootstrap samples. For each treatment arm separately, the assumed event rates will range from assuming that all prematurely censored subjects have a MACE at the time of censoring (corresponding to an infinite event rate for subjects who drop out), to assuming that all prematurely censored subjects complete the study without experiencing the event (corresponding to zero event rate for subjects who drop out). Event rates between the 0 and infinite scenarios, including a censored at random scenario, will be explored by varying the log-hazard rate [Jackson, 2014]. The resulting time to first occurrence of MACE data will be compared across treatment groups using the co-primary Cox proportional hazards model described above, and Rubin's rules [Rubin, 1987] will be used to combine results of the imputed datasets. Graphics depicting hazard ratio and one-sided NI p-value surfaces will be produced using an enhanced tipping point approach [Liublinska, 2014].

Supportive Statistical Analyses
While on-treatment Analysis

 • The while on-treatment MACE analysis will use a structure identical to that described for the co-primary MACE analysis, and will use the time to the first occurrence of while on-treatment adjudicated MACE endpoint (excluding those MACE occurring after subjects permanently discontinued IP). This analysis will use the time period for on-treatment CV endpoints as described in Section 10.6.4. • The HR, associated two-sided 95% CI and one-sided non-inferiority and superiority p-values from this supportive analysis will be included on a forest plot with the co-primary MACE results. • Cumulative time from Randomization to first adjudicated while on-treatment MACE event or end of trial will be evaluated using KM methodology and displayed graphically for the comparison of daprodustat vs. darbepoetin alfa.
COVID-19 Supportive Analyses

 • COVID-19 MACE are identified by the CEC through one of the following statements: 
 ○ Definitive death due to COVID-19 ○ Possible death due to COVID-19 ○ Definite COVID-19 related hospitalization (for MIs and strokes) ○ Possible COVID-19 related hospitalization (for MIs and strokes) • A summary of the number and percentage of subjects having first-occurrence adjudicated COVID-19 MACE will be provided by treatment group. The number and percentage of the types of events that make up the first occurrence of adjudicated COVID-19 MACE will also be provided by treatment group. • The additional supportive analysis of MACE excluding adjudicated COVID-19 MACE, will use a structure identical to that described for the co-primary MACE analysis and will exclude those adjudicated COVID-19 MACE. This analysis will use the time period for follow-up of CV endpoints defined in (see Section 10.6.4). • The HR, associated two-sided 95% CI, and one-sided non-inferiority and superiority p-values from this supportive analysis will be included on a forest plot with the co-primary MACE results. • Cumulative first adjudicated MACE hazard ratio and the upper bound of the 95%CI (Dapro vs Darbe) will be estimated using the same Cox Proportional Hazards model specified in the co-primary MACE analysis (See Section 7.2.2). They will be displayed graphically by calendar date, at every half year mark, starting from Jan2018 or later when the Cox Proportional Hazards model could converge. At each half year mark, subjects who have not had their first MACE will be censored at the date of the half year mark. The graph will also show the cumulative number of first adjudicated MACE by calendar date. A vertical reference line will be used to represent the date the pandemic measures begin in the majority of the countries.
Supportive Expanded Covariate Adjusted Analysis

 • In addition to the baseline categorical values (i.e. Treatment, Current ESA use, Region) that will be adjusted in the co-primary MACE analysis, additional covariates will be included in the Cox Proportional Hazards model: 
 ○ Continuous variables: baseline Hgb, baseline Age, baseline eGFR, logarithm of baseline UACR, baseline albumin ○ Binary variables: sex, history of myocardial infarction, history of stroke, history of heart failure, history of atrial fibrillation, history of diabetes ○ Non-binary categorical variable: race (Asian, Black, White, Other) • For a continuous variable, missing values will be imputed using the mean of all observed values of that variable in the overall study. For a binary variable, missing values will be imputed

Supportive Statistical Analyses

using a Bernoulli distribution with probability as the observed percentage of “Yes” (or “Female”) in the overall study. For race, missing values will be imputed as “Other”.

- This analysis will use the time to the first occurrence adjudicated MACE endpoint, and will use the time period for follow-up of CV endpoints as described in Section 10.6.4.
- The HR, associated two-sided 95% CI and one-sided non-inferiority and superiority p-values from this supportive analysis will be included on a forest plot with the co-primary MACE results.

